6.5 Physical Examination

Physical examinations must be performed by a medically qualified individual, such as a licensed physician, physician's assistant, or a certified registered nurse practitioner.

The physical examination will include the following organ or body system assessments: skin; head, eyes, ears, nose, and throat; lungs; cardiovascular system; abdomen; extremities; lymph nodes.

6.6 Laboratory Assessment

Specific laboratory assessments are listed in Table 9. The total amount of blood to be drawn/collected over the course of the trial (from pre-trial to post-trial visits), including approximate blood volumes drawn/collected by visit and by sample type per subject may vary depending upon clinical course of the subject and length of time on trial. Blood draws will be completed before the subject receives the morning dose of itacitinib. Subjects will be allowed to have lab work performed at external labs in the event that a study visit is conducted remotely, if clinically indicated.

^{**} Related AEs should be followed until resolution, lost to follow up, or judged to be permanent

^{**} Every 12 weeks until death, withdrawal of consent, or the end of the study, whichever occurs first.

^{***} Related AEs should be followed until resolution, lost to follow up, or judged to be permanent

^{****} By telephone, email, visit, or review of EMR

Version 11.0 Page 49 of 72

6.7 Radiographic Evaluations

Subjects will undergo radiographic evaluations to assess disease status at the time points listed below. Timing of radiographic evaluations may be altered based on clinical indication or the discretion of the treating physician.

- Baseline imaging (preferably with FDG-PET/CT, but CT C/A/P or MRI C/A/P are also acceptable) within 8 weeks of starting therapy.
- If imaging was performed as standard of care before signing of the ICF but within 8 weeks of Day 1, then the results from that assessment may be recorded in the eCRF in lieu of a study-specific assessment.
- Response assessment with imaging (investigator choice depending on clinical situation) at week 8 and 16 during the first 4 months of active therapy and every 16 weeks for the remaining active treatment period.
- Imaging will be performed at least every 6 months during the 2 year follow-up period after EOT for patients who came off study for reasons other than progression and who did not start another therapy.

6.8 Unscheduled Visits

An unscheduled visit can occur at any time during the study. The date for the visit and any data (i.e. recording of new AEs) generated must be recorded in subject's chart.

6.9 Subject Withdrawal

6.9.1 Treatment Discontinuation

A subject may be discontinued from treatment regimen using itacitinib and everolimus prior to the expected completion for disease progression, failure to adhere to protocol requirements, failure to obtain everolimus or if the investigator or subject deems it in the subject's best interest to discontinue. The reason justifying study treatment discontinuation should be documented in the study records. Subjects who discontinue the study regimen prior to completion will remain on study for follow-up, unless they withdraw consent. All subjects who receive at least 1 dose of study drug will be followed for toxicity, response and survival unless they withdraw consent.

A subject may be withdrawn from the study (during treatment or follow-up) for reasons including death, subject withdrawal of consent for further follow-up, if the subject is lost to follow-up, or at study termination by study sponsor or by Incyte (drug manufacturer/funding sponsor). If the Sponsor and/or the Investigator should discover conditions arising during the study that indicate the subject should be terminated, an appropriate schedule for termination will be instituted. All subjects who are terminated will complete EOT visit (see section 6.4.6).

The investigator retains the right to terminate his participation in the study at any time. Should this occur, the investigator is to notify the Sponsor in writing.

Page 50 of 72

The sponsor may terminate the study electively or if required by regulatory decision (e.g., FDA request). If the study is terminated prematurely, the sponsor will notify the investigators, the IRB and regulatory bodies of the decision and reason for termination of the study.

Itacitinib + everolimus in HL
Version 11.0
Page 51 of 72

Table 9: Schedule of Study Procedures

Study Phase	Screening		(Cycle 1		Cycles 2-24 ^{d, p}	EOT	Disease Follow-up	Survival Follow-up
Study Days	Day -28 to -1	Day 1	Day 8 ±3	Day 15 ±3	Day 22 ±3	Day 1 ±7			
Visit Number	1	2	3	4	5	6 - 30	31		
Informed Consent	X								
Review Inclusion/Exclusion Criteria	X								
Demographics/Medical History	X								
ECOG PS	X	X	X	X		X	X		
FACT-lym questionnaire		\mathbf{X}^{j}		X		X^q	X		
Physical Examination	X	X	X	X		X^q	X	Xf	
Vital Signs: BP, HR, T, WT, O ₂ Saturation	X	X	X	X		X ^q	X		
Height	X								
Pregnancy Test ^c	X						X		
Prior/Concomitant Medications	X	X	X	X			X		
Confirm that PCP prophylaxis was started ^k		X							
Clinical Laboratory Evaluation ^{a,b, i, m,}	X	X ⁿ	X ^g	X ^g	Xg	$X^{h, n, q}$	X	X ^f	
Antiviral Medication ^o	X								
Cohort Assignment (Phase I)		X							
Dispense Investigational Product		X				Xr			
Everolimus Availability by Subject	X								
Adverse Event Assessment			X	X		X	X		
Assess drug compliance/subject's study calendar			X	X		X	X		
Imaging ^d	X					Xq	X	Xe	
Follow-up anti-cancer treatments									X

Hematology parameters will include a complete blood count: white blood cells, red blood cells, hemoglobin, hematocrit, platelets, neutrophils, lymphocytes, monocytes, eosinophils, basophils and bands (if reported).

Version 11.0 Page 52 of 72

- Serum chemistry parameters will include sodium, potassium, chloride, blood urea nitrogen (BUN), creatinine, glucose, calcium, total protein, albumin, AST, ALT, alkaline phosphatase, total bilirubin, uric acid, LDH, erythrocyte sedimentation rate, and fasting lipid panel. Uric acid and LDH shall be performed during Screening, Cycle 1 Day 1, Cycle 1 Day 8, Day 1 of Cycle 2 through Cycle 24, and EOT. Erythrocyte sedimentation rate shall be performed during Screening, Day 1 of Cycle 1, Day 1 of Cycle 2 through Cycle 24, and EOT. The fasting lipid panel will be drawn only on screening and Day 1 of every 2 cycles (starting with Day 1 Cycle 2).
- A serum pregnancy test will be performed at screening and EOT. Urine pregnancy test will be performed only if pregnancy is suspected during treatment; positive results must be confirmed with a serum pregnancy test. Pregnancy testing will only be required for women of childbearing potential.
- Baseline imaging (preferably with FDG-PET/CT, but CT C/A/P or MRI C/A/P are also acceptable) within 8 weeks of starting therapy. If imaging was performed as standard of care before signing of the ICF but within 8 weeks of Day 1 Cycle 1, then the results from that assessment may be recorded in the eCRF in lieu of a study-specific assessment. Response assessment with imaging (investigator choice depending on clinical situation) at week 8 and 16 during the first 4 months of active therapy and every 16 weeks for the remaining active treatment period. Timing of each imaging is acceptable within +/- 1 week of the protocol specified during first 4 months of therapy and +/- 2 weeks during the remaining active treatment period.
- ^c Imaging will be performed at least every 6 months during the 2 year follow-up period after EOT and then at the discretion of the treating physician.
- In disease follow-up phase subjects who discontinue study treatment for a reason other than disease progression will be followed-up for 2 years from EOT. They should be assessed at least every 3 months (+/- 1 month) using physical exam and standard of care blood work during the first year and every 6 months (+/- 1 month) for the second year. Imaging will be done every 6 months (+/- 1 month) during the 2 years of follow-up.
- g Plus/minus 3 days
- h Plus/minus 7 days
- Viral screening tests to include testing for Hepatitis B (hepatitis B core antibody, hepatitis B surface antigen, hepatitis B surface antibody). Hepatitis C (hepatitis C antibody), HIV (HIV 1 and 2 antibody or viral load)
- Does not need to be repeated if done within 14 days prior starting study treatment
- k PCP prophylaxis (see appendix 13.6 for options) will start before or at Day 1 Cycle 1 and continue until EOT visit.
- EOT visit should occur within 28 days of last dosing.
- m Results may be obtained up to 3 days prior to treatment.
- ⁿ CBC and CMP results must be received before the subject can proceed with mediation treatment.
- ^o Antiviral medication to be taken for the duration of the active trial treatment
- P Additional cycles of investigational treatment may be added if in the opinion of the investigator that the benefit risk ratio for the subject continues to be favorable.
- Not performed when visit is via telemedicine. If clinically indicated, labs may be performed at an outside testing facility.
- r Study medicine will be shipped directly to subject when a telemedicine visit occurs.

Version 11.0 Page 53 of 72

7 STATISTICAL PLAN

7.1 Sample size

Sample size determination: Utilizing 3 + 3 design, 6 to 15 subjects will be enrolled to Phase I portion of the trial (with at least 6 subjects treated at RP2D). Phase II will enroll 8 to 17 subjects depending on expansion needs in the Phase I portion. At least 14 subjects will be treated at RP2D level and evaluable for CR rate. The sample size for phase II was based on a decision between 2 pre-specified hypotheses about the probability of CR rate (p). The null hypothesis H₀: p = 5% reflects a response rate that would be of no clinical benefit compared to everolimus alone, and the alternative hypothesis H_a: p = 25% is a CR rate that might lead to larger, confirmatory studies. Using a Simon 2-stage optimal design, a total of 17 subjects at RP2D will be needed for 80% power at 1-sided alpha = 0.05 level. If by the 16 week visit there are no responders with CR from the first 9 evaluable subjects (at any itacitinib dose level), the null hypothesis will be considered as supported, and the study will be terminated.

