3.1.3 Study Intervention Phase II

Subjects with cHL will receive the recommended Phase II dose (RP2D) of itacitinib in combination with everolimus as determined in Phase 1. Phase II will enroll 8 to 17 subjects depending on Cohort expansion in the Phase I portion. Since 6 of the Phase I subjects will be recruited, treated and followed in the same way as the Phase II subjects, they will be considered as accrued to the Phase II study as well. At least 14 subjects will be treated at RP2D level and evaluable for CR rate. Using a Simon 2-stage optimal design, if there are no responders with CR by the 16 week response assessment from the first 9 evaluable subjects at the RP2D, the null hypothesis will be considered as supported, and the study will be terminated. If there are no CRs in the first several patients (week 8 or 16 assessment), we will suspend the study enrollment and await final response assessment on all 9 patients (until week 16). The study will be considered successful if the total number of subjects with CR is \geq 2 in Phase II.

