7.2.1 Interim Efficacy Analysis

The efficacy analysis is based on Simon 2 stage optimal design and will be performed after the enrollment of the first 9 evaluable subjects. If there are no responders with CR from the first 9 evaluable subjects (at the 8 week or 16 week response assessment, at any itacitinib dose level), the null hypothesis (CR rate of 5% or lower with the new combination) will be considered as supported, and the study will be terminated. If there are no CRs in the first three (3) patients (week 8 or 16), we will suspend the study enrollment and await final response assessment on all 9 patients (6 in Phase I and 3 in Phase II). The study will be considered successful if the total number of subjects with CR is ≥ 2 in Phase II (at the 8 week or 16 week response assessment).

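### The Simon design needs 17 subjects at the RP2D but the plan accepts 14, and the mandatory 0-of-9 stop is defined on two different sets of nine subjects

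*Combined protocol and SAP*

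**What the plan says.** **Number.** Section 7.1 states that "a total of 17 subjects at RP2D will be needed for 80% power at 1-sided alpha = 0.05 level". Shortly before, it says "At least 14 subjects will be treated at RP2D level and evaluable for CR rate", and 3.1.3 repeats that floor. Section 3.1.3 carries Phase I subjects over: "Since 6 of the Phase I subjects will be recruited, treated and followed in the same way as the Phase II subjects". Six carried over plus a Phase II minimum of 8 (7.1, 3.1.3) gives 14. Six plus the minimum of 11 in 4.5 gives 17. Section 4.5 expects 17-20 at the RP2D, and the synopsis gives 8-17 evaluable at the RP2D, apparently the Phase II enrolment range misplaced.

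**Futility nine.**

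| Section | Which nine |
|---|---|
| 3.1.3 | "by the 16 week response assessment from the first 9 evaluable subjects at the RP2D" |
| 7.1 | stop if "there are no responders with CR from the first 9 evaluable subjects (at any itacitinib dose level") |
| 7.2.1 | "at the 8 week or 16 week response assessment, at any itacitinib dose level", but also "await final response assessment on all 9 patients (6 in Phase I and 3 in Phase II") |
| 8.7 | first nine treated at the RP2D in one sentence, any dose level in the next |

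The stop is mandatory wherever it appears. Success is 2 or more CRs in Phase II.

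**The concern.** A trial that ends with 14 evaluable subjects at the RP2D complies with the protocol but does not have the operating characteristics that 7.1 claims. The futility rule leaves no discretion, so two sections could order opposite actions on the same data. On some Phase I paths, 7.1 could close the study on subjects most or all of whom never received the dose under test.

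**Working it through.** **Inputs.** From 7.1: null CR 5%, alternative 25%, one-sided alpha 5%, power 80%, total 17, stage 1 of nine, stop at 0 CR, floor of 14. From 7.2.1 and 7.4: success at 2 or more CRs. From 3.1.2, Table 1: the Phase I paths.

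**1. Reproduce 17.** With a stop at 0 of 9, total n and cutoff c,

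P(success) = Σ(x = 1 to 9) Bin(x; 9, p) × P[Bin(n−9, p) ≥ c−x].

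Among two-stage designs meeting 5% and 80%, the one with the smallest expected size under the null is 0/9 then 3 or more of 17: alpha 4.7%, power 81.2%. The chance of stopping early is 0.95^9 = 63.0% under the null and 0.75^9 = 7.5% under the alternative. Expected size under the null is 9 + 8 × 0.370 = 11.96. The minimax design needs 16 (0/12 then 3 or more: 4.3%, 80.1%). Neither gives 14.

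**2. Try 14, with the same stop.**

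| n | Success at | Alpha | Power |
|---|---|---|---|
| 14 | 2 or more | 13.9% | 87.1% |
| 14 | 3 or more | 2.9% | 71.1% |
| 14 | 4 or more | 0.4% | about 48% |
| 17 | 2 or more | 17.2% | 90.2% |
| 17 | 3 or more | 4.7% | 81.2% |

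No row at 14 meets both targets, so this does not depend on which cutoff is used.

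**3. When do the two nines differ?** Let k be the number of the first nine at any dose who were not at the RP2D. Assume that all Phase I subjects are efficacy-evaluable.

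| Phase I size | Example path in Table 1 | k |
|---|---|---|
| 6 | Cohort 1: 1/3 then 0/3 DLTs | 0 |
| 9 | 3 at Cohort 1, 6 at Cohort 2 | 3 |
| 12 | 6 at Cohort 1, 6 at Cohort -1 | 6 |
| 15 | 3 at Cohort 1, 3 at Cohort 2, 3 more at Cohort 1, 6 at Cohort -1 | 9 |
| 18 | 3 at Cohort 1, 6 at Cohort 2, 3 more at Cohort 1, 6 at Cohort -1 | 9 |

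The nines coincide only on the first path.

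**4. How often do the decisions differ?** The two nines share 9−k subjects, and each has k of its own. They disagree when the shared subjects and one private group have no CR and the other private group has at least one. At an equal CR rate p at every dose:

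P(opposite) = 2(1−p)^9 [1 − (1−p)^k].

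For k = 3 and p = 25%: 2 × 0.0751 × (1 − 0.4219) = 8.7%.

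| k | CR 25% | CR 5% |
|---|---|---|
| 3 | 8.7% | 18.0% |
| 6 | 12.3% | 33.4% |
| 9 | 13.9% | 46.6% |

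**5. Weight over the paths.** Assume the same DLT rate in each cohort, between 5% and 40%, and condition on an RP2D being reached. Table 1 does not say what follows 0/3 and then one DLT in the second three at Cohort 2, so both readings were run. Cohort -1 is taken as acceptable at 0 or 1 DLT in six.

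- The nines coincide in 11.6-22.4% of trials. Opposite decisions occur in 7.6-8.3% at CR 25% and 16.5-20.9% at CR 5%.
- If no subject with a DLT is efficacy-evaluable, the figures are 11.6-27.9%, 5.4-7.9% and 11.4-17.0%.
- Phase I sizes of 6, 9 or 12 make up about 96% or more of these trials.

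**6. Effect on error rates** (3 or more of 17 at the RP2D, any-dose stop). At a CR rate of 25% at every dose, power is 79.5%, 78.2% or 77.4% for k = 3, 6 or 9, and 79.3-79.7% path-weighted, against 81.2% with an RP2D stop. Alpha stays at or below 4.7%. If CR at other doses is assumed lower, path-weighted power is about 76-78% (other doses 15%) or 70-75% (other doses 5%).

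**The case against.** **The 14 may be a rare-path floor.** The planned 23 evaluable subjects, less a 15-subject Phase I, plus six carried over, gives 23 − 15 + 6 = 14. With a Phase I of 12 or fewer, 23 leaves at least 17 at the RP2D. This is a plausible origin and it limits the practical exposure. But the text does not tie the floor to that path: it accepts 14 without condition, next to a statement that 17 are needed.

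**As written, 14 has adequate power.** With 2 or more CRs, power at 14 is 87.1%, and alpha is lower than at 17 (13.9% against 17.2%). That is correct. The written cutoff is a separate and more serious error, and changing 14 to 17 without correcting it would raise alpha. It does not rescue 14, which meets 5% and 80% at no cutoff.

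**The gate is nearly determined.** Section 3.1.3, one sentence of 8.7, and the six-plus-three split in 7.2.1 all point to the RP2D. The any-dose phrase in 7.2.1 and 8.7 might mean only that RP2D subjects still count after a dose reduction. That could reconcile 8.7 with 3.1.3, but nothing in the text says so, and it does not fit 7.1, where the phrase qualifies the nine subjects directly.

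**The disagreement rates look alarming.** At equal CR rates both gates stop equally often, so the disagreement is sampling variation between two sets of subjects, and the power loss is about two points. This stands, and it is why the conclusion rests on an undetermined rule rather than on inflated error rates.

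**Conclusion.** The concern holds and should be fixed before the efficacy rules are applied. The stated 80% and 5% belong to 17 subjects with success at 3 or more. At the accepted 14, power is 71.1% at that cutoff, or alpha is 13.9% at the written one. The two definitions of the futility nine lead to opposite mandatory decisions in roughly 8% of trials at CR 25% and 16-21% at CR 5%, assuming equal CR and DLT rates across doses and all Phase I subjects evaluable. The rates are somewhat lower if subjects with DLTs are not evaluable. The case in which 7.1 stops the study on nine subjects none of whom received the RP2D needs a 15- or 18-subject Phase I, which together make up roughly 4% of trials at most. The two-stage figures are exact. The path weights depend on the assumed DLT range and on how Table 1 is read.

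**What to change.** Use one rule in the synopsis, 3.1.3, 4.5, 7.1, 7.2.1, 7.4 and 8.7:

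- The efficacy set is the first 17 evaluable subjects at the RP2D, including Phase I subjects treated at that dose. Later RP2D subjects are described only.
- Stage 1 is the first nine of these, with a stop at 0 CR. Delete the any-dose wording from 7.1, 7.2.1 and 8.7.
- Replace the floor of 14 with 17 in 3.1.3 and 7.1, or state the alpha and power for 14 instead of 80% and 5%.
- Settle the success cutoff at the same time. At 17, 3 or more is the one that gives the stated 5% and 80%.
- Reconcile the Phase II minimum (8 or 11) and the Phase I range (6-15 or 6-12) with each other and with Table 1, which read literally allows 18.

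The cost is protocol wording. Seventeen at the RP2D after a Phase I of 6, 9 or 12 needs 17, 20 or 23 evaluable subjects, all within the planned 23. A Phase I of 15 or 18 would need 26 or 29, and 29 exceeds the enrolment cap of 28. For those paths, state the lower power rather than enrol more. With 23 evaluable, the RP2D number is 14 (3 or more: alpha 2.9%, power 71.1%) or 23 − 18 + 6 = 11 (1.5%, 54.5%). Even with all 28 evaluable, the 18-subject path leaves 28 − 18 + 6 = 16 (4.1%, 78.5%).

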7.2 Statistical Methods

Time to event data including OS, PFS, DOR will be analyzed using Kaplan-Meier method, treating subjects with no observed death as censored at their last date known to be alive for OS or last documented tumor measurement for PFS and DOR. Median survival and 90% CI will be estimated. Overall survival data will continue to be collected until 75% of subjects have died, have withdrawn consent, or are lost to follow-up.

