4.5 Total Number of Subjects and Sites

The total planned number of evaluable subjects at UPenn will be 23 (including those in Phase I and II portions). To complete Phase I portion utilizing the 3 + 3 design, it is expected that 6 to 12 subjects will be enrolled. For phase II, 11 to 17 subjects will be enrolled. It is expected that total of 17-20 subjects will be treated at the RP2D dose since 3 to 6 patients from Phase I will be treated under the same regimen as Phase II patients. In order to be included in the tolerability review of Phase I, subjects must have received the cohort-specific dose of itacitinib and everolimus for at least 75% of the days during the first 28-day surveillance period or have experienced a DLT. Up to 5 additional subjects may be enrolled to achieve a minimum cohort size should withdrawal or dose interruptions/reductions result in subjects being non-evaluable during Phase I.

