7.5 Secondary Analyses

Lugano Classification (Appendix 13.4) (19) will be used to evaluate efficacy in terms of ORR, CR, PR, SD. Progression-free survival (PFS) will be determined from the enrollment date until the earliest date of disease progression, as measured by investigator assessment of objective radiographic disease assessments per Lugano Classification, or death due to any cause if earlier. Progression-free survival data will be analyzed using Kaplan-Meier method, treating subjects with no observed death or progression as censored at the last valid radiologic assessment visit. Median PFS and 90% CI will be estimated.

Overall survival (OS) will be determined from the enrollment date until death. Survival data will be analyzed using Kaplan-Meier method, treating subjects with no observed death as censored at their last date known to be alive. Median survival and 90% CI will be estimated. Overall survival data will continue to be collected until 75% of subjects have died, have withdrawn consent, or are lost to follow-up.

The DOR is defined as the difference of the end of response and the start of response for subjects who have achieved a response. The start of a response will be the first visit where the subject achieves PR or better based on the Lugano Classification. The end of response will be the first visit where PD is assessed based on the Lugano Classification. Duration of response will be assessed using Kaplan-Meier method for subjects who achieve a response. Median duration and 90% CI will be estimated. Subjects who are still responding at the time of database freeze or discontinuation will be censored at the last valid radiologic assessment visit.

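### Section 7.2 uses absence of death as the only censoring condition for PFS and DOR as well as OS, which contradicts the event definitions in 7.5

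*Combined protocol and SAP*

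**What the plan says.** Section 7.2 (Statistical Methods) covers OS, PFS and DOR in one Kaplan-Meier sentence. Its censoring clause is "treating subjects with no observed death as censored at their last date known to be alive for OS or last documented tumor measurement for PFS". The sentence then applies the tumor-measurement date to DOR too. Progression is not mentioned.

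Section 7.5 (Secondary Analyses) treats each endpoint separately:

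- **PFS event:** "Progression-free survival (PFS) will be determined from the enrollment date until the earliest date of disease progression", "or death due to any cause if earlier".
- **PFS censoring:** "treating subjects with no observed death or progression as censored at the last valid radiologic assessment visit".
- **PFS estimate:** "Median PFS and 90% CI will be estimated". No null value, target or expected median is given.
- **DOR:** "The end of response will be the first visit where PD is assessed based on the Lugano Classification". Subjects still responding at database freeze or discontinuation are censored at their last valid radiologic assessment. Death without progression is not addressed.

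Sections 3.3 and 3.3.2.2 also end DOR at progression. PFS and duration of response are secondary objectives in both phases (2.1.2 and 2.2.2).

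**The concern.** A subject who has progressed and is alive has no observed death. Under the 7.2 wording that subject is censored for PFS at the last tumor measurement, which will often be the progression scan itself. Under 7.5 the same subject is a PFS event. A responder who progresses and stays alive is likewise censored for DOR under 7.2 but has reached the end of response under 7.5. One dataset can therefore give two PFS curves and two DOR curves, both traceable to the plan.

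Censoring at the moment of progression is informative, because it removes the outcome being measured. In a single-arm trial no concurrent control would expose a median that is too long. At stake are the reported median PFS, the median DOR and their 90% intervals.

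**Working it through.** **1. The same subjects under the two rules.**

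| Subject | 7.2 taken literally | 7.5 |
|---|---|---|
| Progressed, alive | PFS censored | PFS event |
| Neither progressed nor died | PFS censored | PFS censored |
| Died without progression | PFS event | PFS event |
| Responder, progressed, alive | DOR censored | Response ended |

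The rules differ for living subjects with documented progression.

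**2. Direction.** The Kaplan-Meier estimate is the product of (1 − d/n) over event times. Suppose 7.2 is applied with the event dated at progression for subjects who later died. Living progressors then leave d at their progression date, and they leave the risk set no earlier than before. Every factor is equal or larger, so the curve is never lower and the median is equal or longer. If the event is instead dated at death, this ordering is not guaranteed in every small dataset. It was upward in every scenario run below.

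**3. Hand example (constructed, not trial data).** There are 17 subjects. Progressions are at months 2 (3 subjects), 4 (4), 8 (4), 11 (2) and 15 (2). Two subjects are censored, at 18 and 22. Of the 15 who progressed, 6 died (2 with progression at month 2, 2 at month 4, 1 at month 8, 1 at month 11) and 9 are alive.

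- 7.5: S(2) = 14/17 = 0.82; S(4) = 10/17 = 0.59; S(8) = 6/17 = 0.35. The median is 8 months.
- 7.2, dated at progression: S(2) = 15/17 = 0.88; S(4) = 0.88 × 12/14 = 0.76; S(8) = 0.76 × 9/10 = 0.68; S(11) = 0.68 × 5/6 = 0.57. There are no later events, so the median is not reached.

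The share progressed and alive here (9/17 = 53%) is higher than in the simulations. The example shows the mechanism, not a likely size.

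**4. Simulated size for PFS.** The plan has no PFS figure to reproduce. Inputs from the documents:

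- N = 17 at the RP2D (7.1: "a total of 17 subjects at RP2D will be needed for 80% power at 1-sided alpha = 0.05 level"); 23 was also run (4.5: "The total planned number of evaluable subjects at UPenn will be 23").
- Scans at weeks 8 and 16, then every 16 weeks (6.7).
- Median OS of about 25 months, a background figure for patients progressing after transplant (1.1).
- Three-year accrual (Study Summary).

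Median time to progression and exponential times are assumptions.

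*Set-up A:* uniform accrual, data cut at month 60, no deaths before progression, 2,000 runs per scenario, N = 17. Medians are in months.

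| Assumed median to progression | 7.5 rule | 7.2, dated at progression | 7.2, dated at death | Progressed and alive at cut |
|---|---|---|---|---|
| 4 | 7.4 | 7.4 | 21.4 | 34% |
| 7 | 7.4 | 11.0 | 24.4 | 33% |
| 12 | 14.7 | 18.4 | 28.1 | 25% |

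Dated at progression, the shifts are 0, 11.0 − 7.4 = 3.6 and 18.4 − 14.7 = 3.7 months. Dated at death, they are 14.0, 17.0 and 13.4 months. N = 23 gives nearly the same values.

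*Set-up B:* independent progression and death times, 48-month cutoff, survival followed for 2 years after progression, N = 17. With events dated at progression, the median moves from 3.7 to 7.4 (assumed 4 months), from 7.4 to 11.0 (assumed 7) and from 7.4 to about 12.5 (assumed 10). PFS events fall from about 17 to about 10 or 11.

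*Sensitivity to follow-up (set-up B, assumed 7 months, dated at progression):* with survival followed to the 48-month cutoff, the median goes from 7.4 to about 8. With an 84-month cutoff it stays at 7.4.

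Scan dates are coarse: 16 weeks / 4.345 weeks per month = 3.7 months. Most of the shifts dated at progression are therefore one scan interval.

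**The case against.** The strongest reply is that the correct rule is already in the plan. Section 7.5 is the only place where PFS is defined. It gives the time origin, the event, the assessor and the censoring rule. Section 7.2 gives neither an origin nor an event, so PFS cannot be programmed from 7.2 alone. Read literally, 7.2 would also contradict every DOR definition in the plan, which suggests that a reference to progression was lost when three endpoints were put into one sentence. An endpoint-specific section would normally prevail over a general one.

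Most of this stands. A reader might infer that the plan as written inflates median PFS. The documents do not support that: it would follow only if 7.2 overrode 7.5, and nothing says it does. A reader might also infer that a go/no-go decision is affected. It is not: PFS has no test or target, it is missing from the secondary endpoint lists in 3.3.1.2 and 3.3.2.2, and futility and success rest on CR alone (7.2.1, 7.4).

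The size is also fragile. It depends on assumed progression times, on how long survival is followed and on where the event is dated. Under some of these settings it is zero.

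The contradiction itself remains. Nothing states that 7.5 takes precedence, and a pre-specified analysis should not depend on the analyst picking the right one of two rules.

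**Conclusion.** The censoring condition in 7.2 is wrong as written for PFS and DOR and conflicts with 7.5. If 7.2 were applied instead of 7.5, median PFS and DOR would be biased upward or unchanged. For PFS, with assumed median times to progression of 4 to 12 months and a background median OS of about 25 months, the illustrative shift is 0 to about 5 months with events dated at progression, and about 13 to 17 months in set-up A with events dated at death. DOR was not simulated; its direction follows from the same argument. If 7.5 is followed there is no bias. The conflict is certain from the text; the size is conditional and is not a forecast for this trial.

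**What to change.** In 7.2, replace the shared clause with one condition per endpoint:

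- **OS:** subjects with no observed death are censored at the last date known alive.
- **PFS:** subjects with neither progression nor death are censored at the last valid radiologic assessment.
- **DOR:** responders with no progressive disease are censored at the last valid radiologic assessment, with an explicit statement of whether death without progression counts as an event or is censored.

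Alternatively, delete the clause from 7.2, refer to 7.5, and add the DOR statement on death there. Correcting PFS alone would leave the same defect in DOR.

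The cost is a few lines of text. Design, sample size, visit schedule and data collection do not change.
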